## 6.9. Concomitant Therapy and eCOA Compliance

The summary and reporting of concomitant therapy and eCOA compliance has been described in the CPMP SAP Version 5. No additional covariates will be considered in the models of weekly rescue medication use.

Concomitant therapy will be reported for the first 4 weeks of the double-blind period (active-treatment phase), and separately for the entire 8 weeks of the double-blind period.

## 6.10. Efficacy Analyses

### 6.10.1. Primary Outcome and Methodology

The analysis of the primary outcome has been described in the CPMP SAP Version 5. The longitudinal model will include API-NRS during the preliminary data entry period ([PDEP], last 7 days prior to randomization at Visit 3) and within each nominal week of the double treatment period as a longitudinal outcome. As noted in Section 4.1, endpoint for the primary analysis is defined as 4 weeks post initial treatment administration.

Calculation of the weekly/bi-weekly time intervals used for analysis of weekly/bi-weekly mean scores from the eCOA device will follow the algorithm described in the CPMP SAP

Section 6.12.1, except that the end of the final interval will be determined based on the last visual analog scale (VAS) collection date, or the last scheduled visit start date if VAS results are missing for the last scheduled visit.

### **6.10.2. Additional Analyses of the Primary Outcome**

Borrowing placebo information by pooling from Studies H0P-MC-NP01 and H0P-MC-NP03 for the evaluation of treatment effect on the mean change from baseline of API-NRS (and secondary outcomes of worst pain intensity as measured by the NRS, Brief Pain Inventory-Short Form [BPI-SF] and VAS) will be performed following the description in CPMP SAP Version 5, Section 6.12.1. Descriptive statistics of primary outcome variables by demographics, disposition, disease characteristics, and treatment administration may be summarized by ISA, in order to examine the population homogeneity assumption between ISAs.

### **6.10.3. Secondary Efficacy Analyses**

Secondary efficacy analyses common to all ISAs within CPMP have been described in the CPMP SAP Version 5. Unless otherwise specified, the time point for secondary endpoint measurements is the same as that for the primary endpoint. Study NP02 will also consider the following secondary analyses.

The BPI-SF is a numeric rating scale that assesses the severity of pain (severity scale), its impact on daily functioning (interference scale), and other aspects of pain (for example, location of pain, relief from medications) in various disease states (Cleeland and Ryan 1994).

This table describes the pain scales and corresponding numeric rating scale used in a modified version of the BPI, validated for pain in diabetic polyneuropathy. Participants will rate their pain severity and how, during the past 24 hours, the pain has interfered with the activities described in this table.

Assessment	Topic	Numeric Rating Scale 0-10
4-item Pain severity	Worst pain in last 24 hours Least pain in the last 24 hours Average pain Pain right now	0 = no pain 10 = pain as bad as you can imagine
7-item Pain interference	General Activity Mood Walking ability Normal work Relations with others Sleep Enjoyment of life	0 = does not interfere 10 = completely interferes

A Bayesian longitudinal mixed-effect model for repeated measures (MMRM) analysis will be performed to evaluate the change from baseline to each postbaseline visit for the mean pain interference scale and the mean pain severity scale. The model will utilize the constrained cell

means model so that a common mean is estimated at the baseline. More details on this approach are provided in the Study CPMP SAP Version 5.

Additional Bayesian MMRM analyses will be used to analyze the change from baseline to each postbaseline visit for:

individual pain interference, and  
individual pain severity scales.

This table describes information included in the model.

Categorical effects	the interaction of treatment and visit (constrained to estimate a common mean at baseline across treatments) average baseline pain severity category (baseline NRS < 7, baseline NRS > 7) pooled investigative site
Continuous covariates	none

Abbreviation: NRS = numeric rating scale.

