### 5.2. Determination of Sample Size

Approximately 150 participants will be randomized in a **CCI** ratio to LY3526318 and placebo, respectively. It is expected that approximately 85%, or 128 participants, will complete the double-blind treatment period of the study. **CCI**

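### In the BPI-SF mean-change models, the baseline-pain category is listed without a visit interaction although baseline is itself an outcome, which can cost a little precision.

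*SAP*

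**What the plan says.** SAP 6.10.3 analyses change from baseline in the BPI-SF mean interference and mean severity scores, and in the individual items (four severity, seven interference), with Bayesian mixed models for repeated measures. The approach is a constrained cell "means model so that a common mean is estimated at the baseline". Baseline is therefore a modelled time point and not a covariate.

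The model table lists three categorical effects: "the interaction of treatment and visit (constrained to estimate a common mean at baseline across treatments"); the "average baseline pain severity category (baseline NRS < 7, baseline NRS > 7"); and pooled investigative site. It lists no continuous covariates. Visit appears only in the treatment term.

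For the rest of the model the SAP points elsewhere: "More details on this approach are provided in the Study CPMP SAP Version 5". That master SAP is not among the documents. SAP 6.1 adds that efficacy is analysed over the first 4 weeks and separately over all 8 weeks, so in the longer fit the same coefficient would extend to Week 8.

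**The concern.** When baseline is one of the outcomes, a covariate entered without a visit interaction shifts the baseline mean and all later means by the same amount. The table therefore assumes that participants in the high and low pain categories differ by as much at Week 4 as at baseline.

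That is unlikely for a category defined by baseline pain. Selecting on a baseline measurement tends to make the gap widest at baseline, and regression to the mean then narrows it. If the gap does narrow, the fitted common gap is wrong at both ends. The misfit goes into the estimated covariance between baseline and later scores, which is what the model uses to adjust for baseline. The covariate can then help less than it should, or do slightly worse than leaving it out. At stake is the precision of 13 secondary mean-change analyses.

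**Working it through.** **Figure in the plan.** SAP 5.2 gives "Approximately 150 participants will be randomized in a" redacted ratio and then "It is expected that approximately 85%, or 128 participants, will complete the double-blind treatment period of the study". 150 × 0.85 = 127.5, which rounds to 128, so this reproduces. The documents give no SD, correlation or precision for BPI-SF, so everything below rests on assumed values.

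**Formula.** Take two time points, baseline (0) and Week 4 (1). Let S be the 2×2 covariance within category, g = (g0, g1) the category gaps, and p the share in the upper category, with v = p(1−p). Assume unstructured covariance, complete data and negligible prior influence.

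- Category-by-visit: the variance of the contrast is proportional to V_full = S11 − S01²/S00.
- Common effect: maximum likelihood gives the single gap γ = (1ᵀS⁻¹g)/(1ᵀS⁻¹1). With d = g − γ, the fitted covariance is S* = S + v·d·dᵀ, and V_common = S*11 − S*01²/S*00.
- No covariate: the same formula with d = g.

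The factor 1/[n·q(1−q)], where q is the share allocated to LY3526318, cancels in the ratios. The redacted allocation therefore does not matter here.

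**Worked case.** Within-category SDs 1.4 and 2.0, correlation 0.5, p = 0.5, gap 2.0 falling to 1.0.

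- S00 = 1.96, S01 = 1.40, S11 = 4.00, so V_full = 4 − 1.96/1.96 = 3.000.
- γ = (2.6×2 + 0.56×1)/3.16 = 1.823, so d = (0.177, −0.823).
- S*00 = 1.968, S*01 = 1.364, S*11 = 4.169, so V_common = 3.224.
- No covariate: 4.25 − 1.9²/2.96 = 3.030.
- Ratios: common to category-by-visit 3.224/3.000 = 1.075 (SE 1.037); common to no covariate 3.224/3.030 = 1.064.

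**Range.** Variance ratio of the common effect to category-by-visit, with the ratio to no covariate in brackets. Baseline gap is 2.0 and SDs are as above.

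| Week 4 gap | corr. 0.3 | corr. 0.5 | corr. 0.7 |
|---|---|---|---|
| 2.0 | 1.000 (0.944) | 1.000 (0.982) | 1.000 (1.000) |
| 1.5 | 1.012 (0.994) | 1.019 (1.018) | 1.031 (1.010) |
| 1.2 | 1.032 (1.026) | 1.048 (1.045) | 1.078 (1.025) |
| 1.0 | 1.049 (1.048) | 1.075 (1.064) | 1.123 (1.038) |
| 0.5 | 1.110 (1.103) | 1.167 (1.114) | 1.276 (1.079) |
| 0 | 1.192 (1.153) | 1.296 (1.165) | 1.490 (1.125) |

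**Gaps tied to a cut at 7.** Assume baseline API-NRS has mean 6.3 and SD 1.2. Then z = 0.7/1.2 = 0.583, p = 0.280 and v = 0.2015. Further assume overall BPI severity SD 1.25-1.5 at baseline and 2.0 at Week 4, overall correlation 0.33-0.43, and a gap of 1.9 falling to 1.1-1.5. With S equal to the overall covariance minus v·g·gᵀ, the variance ratio to category-by-visit is 1.006-1.039. The ratio to no covariate is 0.969-1.035. A three-visit simulation under similar assumptions (n = 150, 2:1, at least 7 as the upper category, 5,000 runs in each of four settings) gave 1.00-1.02 against category-by-visit.

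**Bias.** A simulation with n = 128, three visits, 1:1 and 2:1 allocation and 2,000 runs per setting put the SE ratio at 0.997-1.132. The top of that range occurs when the gap vanishes. The bias of the treatment contrast was at most 0.014 points. Simulation error for that mean is about 0.33/√2000 = 0.007, so this cannot be told from zero.

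**The case against.** **The master SAP may settle it.** SAP 6.2 and 6.10.3 defer the adjustment strategy and model detail to CPMP SAP Version 5, which may already cross the category with visit. That stands as a limit on the finding. But the NP02 table states what the model includes and writes out a visit interaction for treatment, so the two documents would then need aligning.

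**The gap need not narrow.** If the SD of the score rises from 1.4 to 2.0, the gap narrows only when the score's correlation with baseline NRS falls below 1.4/2.0 = 70% of its baseline value. For interference items, which are not what the category is cut on, the narrowing is less certain still. This stands, and is why the loss is a possibility and not a certainty.

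**The effect is small and secondary.** Correct. The table does not govern the primary analysis, and no bias arises.

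Three stronger readings are tempting, and the documents do not support them.

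- *Participants at exactly 7 have no category and drop out.* The available text does read below 7 and above 7. But comparison signs are missing or garbled elsewhere in this SAP text (the neuropathy instrument cut in 6.7, eGFR category 1 in 6.12.4, the liver criteria in 6.17). The upper category may read at least 7 in the signed version. Nothing says such participants would be excluded. This is a query only.
- *Every BPI-SF comparison loses precision.* The 30%, 50% and 70% responder analyses use a separate categorical repeated measures model, and time to response follows the master SAP. This table specifies neither.
- *Listing no continuous covariates throws baseline information away.* Each participant's baseline BPI-SF score is already in the outcome vector.

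**Conclusion.** The point holds in limited form. As listed, the 13 BPI-SF mean-change models constrain the baseline-pain category to the same effect at baseline and afterwards, which is implausible for a category cut on baseline pain. The likely cost is roughly 0-6% of the variance of the Week 4 contrast. At 6%, that is worth 128 × (1 − 1/1.06) ≈ 7 of the 128 expected completers.

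This range covers the settings tied to a cut at 7. It also covers the grid while the within-category correlation is at most 0.5 and a 2-point gap stays at 1.2 or more. The loss is nil if the gap is constant. It reaches 7-12% if the gap halves at correlations of 0.5-0.7, and exceeds that only if most of the gap disappears. Against no covariate, the listed term ranges from about 6% better to 6% worse for Week 4 gaps of 1.0 to 2.0.

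All sizes rest on assumed SDs, correlations and gaps, and on likelihood calculations standing in for the Bayesian fit without the site term. The randomised contrast stays essentially unbiased.

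**What to change.** In the SAP 6.10.3 model table:

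1. Replace the baseline-pain category main effect with category-by-visit, baseline included. If CPMP SAP Version 5 already specifies this, make the table match it and cite the section.
2. Confirm the cut, and state the upper category as at least 7 if that is what the signed SAP intends.
3. Optionally, add the continuous 7-day mean by visit. It is already in hand, since for the primary analysis "The longitudinal model will include API-NRS during the preliminary data entry period". The further gain is small: about 1-4% of variance relative to category-by-visit in four assumed settings.

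The main change costs SAP wording and one extra parameter per post-baseline visit in each model, so at most four through Visit 7. It needs no new data and does not touch the primary analysis. It should be made before unblinding.

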### Other Secondary Analysis

The proportion of participants in each treatment group meeting prespecified binary efficacy outcomes will be calculated for each postbaseline time point and will be used to compare treatment groups. The prespecified binary efficacy outcomes include the proportion of participants:

- with a reduction of at least 30%, 50%, and 70% from baseline as measured by the mean pain interference score
- with a reduction of at least 30%, 50%, and 70% from baseline as measured by the mean pain severity score
- with a reduction of at least 30%, 50%, and 70% from baseline as measured by the individual interference scores, and
- with a reduction of at least 30%, 50%, and 70% from baseline as measured by the individual severity scores.

A Bayesian pseudo-likelihood-based categorical repeated measures model will be used to estimate the proportion of participants in each treatment group meeting the prespecified threshold for each postbaseline time interval up to Week 4 (or visit up to Visit 5) and separately up to Week 8 (or visit up to Visit 7). These estimates will be used to compare treatment groups. More details on this approach are provided in the CPMP SAP Version 5.

In addition, time to first treatment response from baseline based on the prespecified binary thresholds above will be assessed. Analyses will be conducted according to the time to event analyses specified in the CPMP SAP Version 5.

## 6.11. Bioanalytical and Pharmacokinetic/Pharmacodynamic Methods

The observed plasma concentrations for LY3526318 over time will be reported in tabular format using descriptive statistics and graphically using individual and mean concentration time plots. Nominal protocol time will be used for the descriptive summary and mean plot and actual time for the plots of individual data.

Additional analyses may be conducted, as deemed necessary upon review of the data. For example, graphical and/or model-based pharmacokinetic (PK) and PK-pharmacodynamic (PD) analyses to explore exposure-response relationships for safety and/or efficacy may be conducted. Data from this study may be pooled with data from other studies, if appropriate.

## 6.12. Safety Analyses

The general analysis of safety has been described in the Study CPMP SAP Version 5. However, additional ISA-specific safety considerations are described in the sections below.

### 6.12.1. Extent of Exposure

Duration of exposure (defined as time since first dose of study treatment to last dose of study treatment in days) to study drug will be summarized by treatment group using descriptive statistics; the summary will also include the total exposure in patient years. Extent of exposure will be reported separately for the first 4 weeks (active treatment) and the last 4 weeks (post-active treatment) of the double-blind period. All patients will receive placebo starting the day of Visit 5.

Duration of exposure (days):

1. For the first 4-week active treatment period:  
= Date of last dose during the active treatment period   Date of first dose for the active treatment period + 1
2. For the last 4-week post-active treatment period:  
= Date of last dose during the post-active treatment period   Date of first dose for the post-active treatment period + 1

Total exposure in patient years will be calculated as follows:

Total exposure in patient years = Sum of duration (days) of exposures for all patients in the treatment group/365.25.

### 6.12.2. Adverse Events

The general analysis of adverse events has been described in the CPMP SAP Version 5.

This ISA will report TEAEs for the first 4 weeks as well as post-active-treatment-emergent AEs (PTEAEs) for the last 4 weeks of the double-blind period. For TEAEs in the first 4 weeks of the double-blind period (active treatment phase), the baseline will be prior to first dose date.

A PTEAE is defined as an event that first occurs or worsens in severity after active-treatment phase (after Visit 5) and on or before study discontinuation. The Medical Dictionary for

Regulatory Activities (MedDRA) Lowest Level Term (LLT) will be used in the post-treatment-emergent computation. The maximum severity for each LLT during the active-treatment period (Visits 3 through 5) will be used as a reference.

The baseline of PTEAE is from the first dosing date to Visit 5. The post-active-treatment phase will be included as postbaseline for this analysis. While unusual, it is possible to have a missing severity for events. For events with a missing severity during the baseline period, it will be . . . . . or determining post-active treatment-emergence. Events with a missing severity during the post-active . . . . . PTEAEs will be determined by comparing with active-treatment period.

PTEAEs will be summarized by Preferred Term and by Preferred Term within System Organ Class in participants who received LY3526318.

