## 5. Study Design

### 5.1. Summary of Study Design

The CPMP protocol provides a summary of the overall study design for the chronic pain master protocol. ISA-specific study design is provided in the NP02 protocol.

In this ISA, patients in the LY3526318 treatment arm receive LY3526318 for the first 4 weeks of the double-blind period (active-treatment period) and switch to placebo for the last 4 weeks of the double-blind period (post-active-treatment period) starting on the day of Visit 5. Placebo patients receive placebo for the entire 8-week double-blind period. Additional details of the study design may be found in the ERB supplement for Study NP02.

For the analyses listed in this SAP, except for treatment compliance, we define active treatment period and post-active treatment period as follows. The first 4 weeks of the double-blind period (active treatment period) ends at the day of Visit 5. The last 4 weeks of the double-blind period (post-active treatment period) begins the day after Visit 5.

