## 6. A Priori Statistical Methods

### 6.1. General Considerations

The estimand for the primary clinical question of interest has been described in the CPMP SAP Version 5.

Unless otherwise specified, efficacy analyses will be conducted for the first 4 weeks of the double-blind period (active treatment phase) and separately for the entire 8-week study. A post-active treatment population will be used for analyses of the last 4 weeks of the double-blind period (post-active-treatment phase) and will include all patients who do not discontinue at or prior to Visit 5. For treatment-emergent adverse events (TEAEs), participants in the post-active treatment population will be analyzed according to the treatment they receive during the active treatment phase. Adverse event (AE) analyses will be reported for the first 4 weeks of the double-blind period (active treatment phase) and separately for the last 4 weeks of the double-blind period (post-active treatment phase). Some AEs may be reported for the entire 8 weeks, if necessary. Laboratory, electrocardiogram, and vital sign results will be reported for the active-treatment phase and separately for the entire 8-week study.

Other general considerations for analyses are described in the CPMP SAP Version 5.

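### The SAP's post-switch adverse event summary names only LY3526318 participants, although Section 6.1 defines the weeks 5 to 8 population across both arms

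*SAP*

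**What the plan says.** SAP Section 5.1 describes a switch within the double-blind period. The LY3526318 arm takes active drug for 4 weeks and placebo from the day of Visit 5. For the other arm, "Placebo patients receive placebo for the entire 8-week double-blind period".

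SAP Section 6.1 creates a post-active treatment population for analyses of the last 4 weeks. It "will include all patients who do not discontinue at or prior to Visit 5". For treatment-emergent adverse events, "participants in the post-active treatment population will be analyzed according to the treatment they receive during the active treatment phase". The same section says that adverse events are reported for the first 4 weeks and separately for the last 4.

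SAP Section 6.12.2 defines a PTEAE as an event that starts or worsens after Visit 5. It sets the comparison level as follows: "The maximum severity for each LLT during the active-treatment period (Visits 3 through 5) will be used as a reference". Neither the definition nor this reference is tied to an arm. The display rule is: "PTEAEs will be summarized by Preferred Term and by Preferred Term within System Organ Class in participants who received LY3526318".

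SAP Section 6.12.1 reports exposure separately for the two periods, and duration of exposure "to study drug will be summarized by treatment group using descriptive statistics". For everything general, SAP Section 6.12 points elsewhere: "The general analysis of safety has been described in the Study CPMP SAP Version 5". That document was not available.

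**The concern.** The population and grouping rule in Section 6.1 describe a two-group display for weeks 5 to 8. Section 6.12.2, the only place in the two documents that specifies the PTEAE table, describes one group. It gives no reason for the narrower scope and does not mention the Section 6.1 population.

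What is at stake is how post-switch events can be read. Coming off LY3526318 could bring withdrawal or delayed effects, and the PTEAE table is the display built to show them. Participants with diabetic neuropathic pain will also report new events over any 4 weeks for unrelated reasons. The design supplies the group that would show this background: participants who stay on placebo, under the same blind and visit schedule. If the table omits them, a count in the LY3526318 column cannot be divided into background and excess.

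**Working it through.** **Comparison of the text.** The main finding rests on wording, not arithmetic.

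| Item | SAP 6.1 | SAP 6.12.2 |
|---|---|---|
| Who is included in weeks 5 to 8 | All patients continuing past Visit 5, either arm | LY3526318 recipients |
| Grouping | Active-phase treatment (stated for TEAEs) | None stated |
| Event definition | Not given here | Not arm-specific |

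Grouping by active-phase treatment serves a purpose only if there is more than one group. The rule says TEAEs, not PTEAEs. But it concerns the post-active population, and Section 6.12.2 reports adverse events in that phase as PTEAEs, so they are its natural subject.

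**The plan's own figure.** SAP Section 5.2 states: "It is expected that approximately 85%, or 128 participants, will complete the double-blind treatment period of the study". Check: 150 × 0.85 = 127.5, rounded up to 128. It reproduces.

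**Inputs for the size of the issue.**
- Participants entering weeks 5 to 8: not given. Assumed between 128 (expected completers) and 150 (all randomized).
- Allocation ratio: redacted. Assumed 1:1 or 2:1 (LY3526318:placebo); 3:1 is added as a check.
- Background rate *p* per Preferred Term over 4 weeks: not given. Assumed 5% to 10%.

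**Background count in the LY3526318 column** = n × p.
- Lowest: 64 × 0.05 = 3.2. The binomial 95% range is 0 to 7.
- Highest: 100 × 0.10 = 10.0. The binomial 95% range is 5 to 16.

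**Precision if placebo is shown.** The 95% half-width of the arm difference is 1.96 × √[p(1 − p)(1/n₁ + 1/n₂)]. For example, with 64 per arm and p = 0.05: 1.96 × √[0.0475 × (1/64 + 1/64)] = 0.0755.

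| LY3526318 / placebo | p = 0.05 | p = 0.10 |
|---|---|---|
| 64 / 64 | 0.0755 | 0.1039 |
| 75 / 75 | 0.0698 | 0.0960 |
| 85 / 43 | 0.0799 | 0.1100 |
| 100 / 50 | 0.0740 | 0.1018 |

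The range is 0.070 to 0.110. At 3:1 with 128 participants (96 / 32) and p = 0.10, the half-width is 0.120, slightly above that range.

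**Participants left out.** Of 128 expected completers, a table limited to LY3526318 omits about 64 at 1:1 (one half), 43 at 2:1 (one third) or 32 at 3:1 (one quarter).

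**The case against.** The strongest counter-argument is that a specific section may narrow a general one without contradicting it. Section 6.12.2 does not say that only LY3526318 participants will be shown. Read together with Section 6.1, a by-arm adverse event display for weeks 5 to 8 may already be intended, with the PTEAE sentence adding a view focused on the drug. The restriction may also be deliberate, since only the LY3526318 arm comes off active treatment. The master SAP (CPMP SAP Version 5) may fix the columns. Other displays keep placebo information: the registry summary is by treatment group (Section 6.19), the totality-of-evidence safety analysis may cover the post-active period (Section 6.17), and some events may be reported for the whole 8 weeks (Section 6.1).

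Part of this stands. The master SAP could settle the matter, and a deliberate choice cannot be excluded. Exposure by treatment group in Section 6.12.1 is a different table and is weak evidence about this one. The sizes above rest on assumed rates and allocation.

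The rest does not remove the problem. Neither document gives a reason for the restriction. None of the other displays is a PTEAE table, and the Section 6.17 period and 8-week options are optional. A programmer who follows the trial-specific sentence would produce a table without placebo. That only one arm stops active drug is a reason to show the other arm beside it, because that arm supplies the background rate.

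**Conclusion.** The concern holds. Sections 6.1 and 6.12.2 of the SAP do not agree on who appears in the weeks 5 to 8 adverse event summary, and Section 6.12.2 followed as written leaves out the concurrent blinded comparator. Under the stated assumptions (128 to 150 participants, 1:1 or 2:1 allocation, 5% to 10% background), about 3 to 10 LY3526318 participants per Preferred Term row would be expected from background alone, with nothing in the table to show it.

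The gain from a placebo column is real but limited. It supplies a background rate; with half-widths of about 7 to 11 percentage points, it would not reliably detect a moderate excess. Placebo adverse event data are collected in any case, and no efficacy result, sample size or error rate is touched. The change should be made. Confidence is medium, because the CPMP SAP Version 5 could not be consulted.

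**What to change.** Reword the display sentence in SAP Section 6.12.2, for example: PTEAEs will be tabulated by Preferred Term, and by Preferred Term within System Organ Class, for each active-phase treatment group (LY3526318 and placebo) in the post-active treatment population. The existing reference severity from Visits 3 through 5 can be applied to placebo participants unchanged.

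Add that the comparison is descriptive, because the population is conditioned on remaining in the study past Visit 5 and precision is limited. If the CPMP SAP Version 5 already sets a by-arm display, cite it in Section 6.12.2. If the restriction to LY3526318 is intended, state it and the reason in both sections.

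The cost is one reworded sentence and one table column, with no new data collection.
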